3.6.2 Immunogenicity (IM) Analyses

Samples collected during treatment and post-treatment period, including early termination and unscheduled samples for IM assessment as specified in the study protocol will be analyzed for ADA. However, plasma samples collected at other time points (or for PK purposes) may also be potentially evaluated if deemed of further interest and warranted by the pharmacokinetic scientist. Samples that are confirmed IM positive are subjected for titering, which may include but not limited to the samples collected on Days 85, 176, 358, 540, 722, or 1086 during treatment period.

An evaluable sample will be designated 'IM positive' based on both positive screening and confirmation assay results (i.e., confirmed positive result); otherwise, the sample will be deemed 'IM negative'. Sample IM results (screen positive/negative, confirmed positive/negative or unevaluable, and when applicable, titer of anti-ISIS 420915 antibodies) during and after treatment with study drug (ISIS 420915) (sample IM status) will be listed by the subject's prior treatment in the parent study, dose, and study day.

Patient IM status: Study patients will be given 'IM positive' status if they have at least one confirmed positive sample result at any time during the treatment or post-treatment evaluation periods. Study patients will be given 'IM negative' status if all evaluated IM sample results during the treatment and post-treatment evaluation periods are IM negative and they have at least one evaluable IM result collected post study drug treatment. Otherwise, a study patient will be given 'unknown' IM status. Subject IM results will be listed by treatment group of the parent study and dose for all evaluable patients, which will include but may not be limited to: patient IM status (positive, negative or unknown), the day associated with the first positive IM status emerged since receiving ISIS 420915 treatment (T_{first}, i.e., onset of ADA development as described below), the last positive IM status observed (T_{last}), the last evaluable IM sample collected (T_{last sampling}), peak titer, and time to reach peak titer.

Onset of immunogenicity: The onset (T_{first}) of anti-ISIS 420915 antibodies for OLE study will be derived as the difference between the date when first immunogenicity sample becomes confirmed positive (i.e., positive sample IM status) and Day 1 of ISIS 420915 plus one.

 If a patient has confirmed positive IM samples detected on or prior to Day 1 of ISIS 420915, e.g., pre-existing antibodies cross-react with ISIS 420915, the onset in the OLE study for that patient would be less or equal to 0 (≤0).

Other immunogenicity data analysis (e.g. classification as persistent or transient status, etc.) may be performed as described below (Shankar et al, 2014) if deemed warranted at the discretion of the pharmacokineticist, medical monitor, and/or biostatistician.

Transient ADA response will be defined as:

- Treatment-induced ADA detected only at one sampling time point during the treatment or followup observation period (excluding the last sampling time point, which ought to be considered persistent unless shown to be undetectable at a later time) or
- Treatment-induced ADA detected at two or more sampling time points during the treatment (Including follow-up period if any), where the first and last ADA-positive samples (irrespective of any negative samples in between) are separated by a period less than 16 weeks, and the subject's last sampling time point is ADA-negative.

Persistent ADA response will be defined as:

- Treatment-induced ADA detected at two or more sampling time points during the treatment (Including follow-up period if any), where the first and last ADA ositive samples (irrespective of any negative samples in between) are separated by a period of 16 weeks or longer or
- Treatment-induced ADA incidence only in the last sampling time point of the treatment study period or at a sampling time point with less than 16 weeks before an ADA-negative last sample.

The sample IM incidence (number) and incidence rate (percent) at each evaluated study time point, and for the overall treatment and post-treatment evaluation period, as well as subject IM incidence and incidence rate, will be determined and appropriately summarized by treatment group of the parent study, as the total number of and percentage of evaluated subjects with IM negative, positive, and unknown status. Subjects with positive IM status may further be classified as transient or persistent status if applicable, with incidence and incidence rate being transient or persistent appropriately summarized. Furthermore, onset, titer over time, peak titer of the ADA response, and time to reach peak titer, if applicable, will be also appropriately summarized (using descriptive statistics) as median, quartiles (25% and 75%), and range and presented graphically, if deemed appropriate, by treatment group of the parent study (e.g., summarized at each evaluated study time point and overall; summarized by observed peak titer values from the individual IM positive patients; etc.).

- Onset in days = The date of first sample has "positive" sample IM status Day 1 of ISIS 420915
 +1;
- Time to reach peak titer in days = The date of peak titer observed- Day 1 of ISIS 420915 +1;

In addition to PK assessments (Section 3.6.1), selected efficacy (Sections 3.4 to 3.5) and safety (Section 3.3) assessments will also be further stratified by patient IM status (i.e., patient IM status being positive, negative, or unknown) and presented in tables and/or graphically, as deemed appropriate or warranted by the designated study pharmacokineticist, medical monitor, and/or biostatistician. Efficacy measures to be stratified by patient IM status will include, but may not be limited to, TTR level, mNIS+7, and Norfolk QOL-DN score. Safety measures to be stratified by patient IM status will include, but may not be limited to, AEs, and lab tests for hematology and kidney functions.

Other stratifications (e.g., based on antibody titer, onset of ADA, etc.) of selected PK, efficacy and safety assessments may also be performed if deemed warranted at the discretion of the pharmacokineticist, medical monitor, and/or biostatistician.

4. Sample Size

No sample size calculations were performed as this is an extension study to the double-blind, placebo-controlled ISIS 420915-CS2 study. Approximately 135 patients were planned to be eligible to enroll into this present OLE study.

5. Interim Analyses

Database closing and locking will be done at the following milestones:

- 1. When all patients in the parent study have completed the EOT assessments, the OLE study database will be cleaned and will be unblinded according to CS2 unblinding plan. Therefore, all treatment information is available for this OLE study to the team specified in the CS2 unblinding plan. This interim analysis will be used to support the FAP regulatory file. For this interim analysis the data cut-off date utilized was prior to the last subject completing EOT assessments in the parent study CS2 to allow sufficient time for data cleaning prior to closing the database for analysis.
- After all patients complete the study (at EOS). This will be considered the final analysis of this OLE study.

Additional closing and locking may be done to support additional interim analyses, with the timing of the database closing and locking coinciding with regulatory requirements or study milestones.

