- The Immunogenicity (IM) on-study period for the OLE study spans the time the first dose of ISIS420915 in the parent study and ends on the day of the patient's last contact date within the OLE study. This period is for defining patient IM status (Details in section 3.2.1.1.6).

3.2.1.1.5 Durations of study drug exposure and total dose of ISIS 420915:

Durations of overall drug exposure (days) across both studies will be derived as the difference in
days between the date of the last dose of ISIS 420915 and Day 1 of ISIS 420915 plus one. For
patients who are not enrolled in the OLE study, the last dose of ISIS 420915 is administered in the
parent study; for patients who are enrolled in the OLE study, the last dose of ISIS 420915 is
administered in the OLE study.

The total dose of study drug during the treatment period for either the parent study or the OLE study will be computed for patients receiving ISIS 420915 by summing the dose administered between **Day 1 of ISIS 420915** and the last dose date in the parent study for patients who are not enrolled in the OLE study or the last dose date in the OLE study for patients who are enrolled in the OLE study. Total dose will be summarized in milligrams as part of longitudinal safety analysis.

• Duration of drug exposure in OLE study (days) will be derived as the difference in days between the date of the last dose of ISIS 420915 in OLE study and **CS3 Study Day 1** plus one.

The total dose of study drug during the treatment period for the OLE study will be computed for patients receiving ISIS 420915 in the OLE study by summing the dose assigned between **CS3 Study Day 1** and the EOT date or date of early termination in OLE study. Total dose will be summarized in milligrams.

3.2.1.1.6 *Immunogenicity (IM):*

- For subjects with negative IM status in the parent study, the onset (T_{first}) of anti-ISIS 420915
 antibodies in OLE study will be derived as difference in days between the date when first
 immunogenicity sample becomes confirmed positive (i.e., positive sample IM status) in OLE study
 and Day 1 of ISIS 420915 plus one.
- For subjects with positive IM status in the parent study, the onset (T_{first}) of anti-ISIS 420915 antibodies in the parent study will be used as the onset of the OLE study.

3.2.1.1.7 BMI and mBMI:

• Body mass index (BMI) will be computed using the formula:

BMI = (weight in kilograms) / [height in cm / 100]²

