Safety Endpoints: ERG and ophthalmology examinations	-Listings -On-treatment summary tables (CS3) -Post-treatment summary tables	-On-treatment (CS3 period): CS3 Study Day ls Date of assessment 5 Last dose date+ 28 days -Post-treatment: Date of assessment> last dose date+ 28 days -Visit defined by analysis visit window
Safety Endpoints: abnormal lab, worst ECG, meeting Stopping rule	-Listings -On-study summary tables (CS3)	-Abnormal lab analyses described in Sections 3.3.4.1 to 3.3.4.3 include post-baseline data collected from CS3 Study Day 1 up to the day of the patient's last contact date within the study
Safety Endpoints: AE	-Listings -On-treatment (CS3) summary tables -On-study (CS3) summary tables	-On-treatment: CS3 Study Day ls Date of assessment 5 Last dose date + 7 days -On-study summary tables includes all treatment emergent adverse event (TEAE) in the OLE study, including those with onset dates> last dose date + 7 days
Selected Safety Endpoints: abnormal lab and AEs	- Longitudinal safety summary for overall parent study and OLEstudy	- Longitudinal safety summary for overall parent study and OLE study include data collected from the first dose of ISIS 420915 in the parent study and ends on the day of the patient's last contact date within the study, (1) for subjects who enrolled in the OLE study, it is the last contact date within the OLE study; (2) for subjects who are not enrolled in the OLE study but had been administered ISIS 420915 in the parent study, it is the last contact date within the parent study.
Concomitant medications	-Listings -On-treatment (CS3) summary tables -On-study (CS3) summary table	-On-treatment: CS3 Study Day ls Date of assessment s Last dose date + 7 days -On-study summary tables includes all concomitant medication in the OLE study, including those with onset dates > last dose date+ 7 days
Immunogenicity	-Listings -On-study (CS2 and CS3)	-On-study summary/analysis tables include data collected from the CS2 Study Day 1 up to the day of the

Endpoint type	Output type	Comment/definition
	summary/ analysis tables	patient's last contact date within the study (showing both CS2 visits and CS3 visits) -Visit defined by analysis visit window.
PK	-Listings -On-study (CS3) summary/ analysis tables	-Summary/analysis tablesinclude data collected from CS3 Study Day 1 up to the day of the patient's last contact date within the study -PK concentration will be summarized based onnominal scheduled visits (showing CS3 visits)

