9.2.2.2 Study Period Definition (On-Treatment, Post-Treatment and On-Study)

On-Treatment

- For efficacy endpoints except BMI, mBMI and PD, on-treatment period starts from ISIS
 420915 Study Day 1 until 52 days after the last dose of ISIS 420915.
- For BMI, mBMI, PD and Safety endpoint ERG, on-treatment period is from ISIS 420915 Study
 Day 1 until 28 days after the last dose of ISIS 420915
- For other Safety endpoints except ERG, on-treatment period is from ISIS 420915 Study Day
 until 7 days after the last dose of ISIS 420915

Post-Treatment

Post-treatment period starts on the day after the on-treatment period and ends on the day
of the patient's last contact date within the study.

On-Study

On-Study starts from ISIS 420915 Study Day 1 until the patient's last contact date.

Of note, the definition above only apply for CS2 and CS3 combined data summary, which is not conflict with section 3.2.1.1.4

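### The SAP's antibody-onset and IM-status rules disagree for positives at or before the first ISIS 420915 dose, mainly in former-placebo patients

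*Combined protocol and SAP*

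**What the plan says.** SAP 3.6.2 derives onset as the difference between the date when a sample first "becomes confirmed positive (i.e., positive sample IM status) and Day 1 of ISIS 420915 plus one". The summary rules later in that section repeat the origin and the added day for onset, and use them for the titer as well: "Time to reach peak titer in days = The date of peak titer observed- Day 1 of ISIS 420915 +1". For antibodies already present, the section takes the case "If a patient has confirmed positive IM samples detected on or prior to Day 1 of ISIS 420915" and states that "the onset in the OLE study for that patient would be less or equal to 0 (≤0"). The description of the patient listing, also in 3.6.2, instead treats the first positive as one that appears once ISIS 420915 has been given.

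SAP 3.2.1.1.6 splits patients by parent-study result. Those negative there get the formula, applied to their first positive OLE sample. The other rule opens "For subjects with positive IM status in the parent study, the onset" and goes on to reuse the parent-study onset in the OLE study. It does not mention treatment arm. SAP 3.2.1.1.1 places Day 1 of ISIS 420915 at the first OLE dose for former-placebo patients, and defines CS2 Study Day 1 as the first dose of either active drug or placebo.

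Three sections give a time period:
- SAP 3.2.1.1.4 says the IM on-study period serves to define patient IM status, and starts it at the first ISIS 420915 dose in the parent study.
- SAP 3.2.1.4 governs the OLE tables: "On-study summary/analysis tables include data collected from the CS2 Study Day 1 up to the day of the" patient's last contact, with visits from both studies shown.
- SAP 9.2.2.2, for combined CS2 and CS3 summaries only, says: "On-Study starts from ISIS 420915 Study Day 1 until the patient's last contact date".

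**The concern.** A confirmed positive at or before the first active dose cannot have been caused by the drug. A plan that reports antibody onset and incidence needs one rule for such samples. This SAP has several, and they give different answers for the same sample. The former-placebo group is where this matters most, because it is the only group whose first exposure to ISIS 420915 falls within this study.

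More than the onset table depends on it. Patient IM status stratifies the trough concentrations in SAP 3.6.1. Under 3.6.2 it also stratifies selected efficacy and safety outputs, including TTR, mNIS+7, Norfolk QOL-DN, adverse events, and hematology and kidney laboratory tests. If a placebo-period sample makes a patient IM positive, that patient moves to a different stratum in all of these.

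**Working it through.** **Step 1: the Day 1 sample.** The formula in SAP 3.6.2 is onset = sample date − Day 1 of ISIS 420915 + 1. The SAP's stated result for a positive on or before Day 1 is ≤ 0.

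- Sample on Day 1: 0 + 1 = 1. The stated result is not reproduced.
- Sample one day before: −1 + 1 = 0. Reproduced.
- Sample two days before: −2 + 1 = −1. Reproduced.

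The stated result therefore holds only for samples strictly before Day 1. Without the added day, the three values would be 0, −1 and −2 and the statement would hold throughout, but the SAP writes the added day in both 3.2.1.1.6 and 3.6.2.

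**Step 2: how often Day 1 can arise.** In protocol Appendix A the immunogenicity row begins at Week 7, whereas the PK trough row begins at Week 1, pre-dose. For former-placebo patients, a Day 1 antibody result therefore needs an unscheduled test or use of the PK plasma, which SAP 3.6.2 allows. For former-active patients Day 1 lies in CS2, and if they were positive there, 3.2.1.1.6 takes their onset from that study. Few Day 1 cases are expected.

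**Step 3: the carry-over for former-placebo patients.** Two rules apply to the same placebo-period positive. The documents do not give the origin of the parent-study onset, so the following is an illustration under stated assumptions:

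- The parent-study onset is counted from CS2 Study Day 1 (assumed).
- The last CS2 dose is at Week 65, nominally Day 449 in SAP Appendix 3. The first OLE dose follows 1 to 4 weeks later (protocol 3.4.1), at CS2 Day 449 + 7 = 456 to 449 + 28 = 477.
- The positive sample is at CS2 Day 85, 240 or 449 (assumed; the CS2 antibody schedule is not in the documents).

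| Positive at CS2 day | SAP 3.6.2 formula | Carried-over onset |
|---|---|---|
| 85 | 85 − 456 + 1 = −370 to 85 − 477 + 1 = −391 | 85 |
| 240 | 240 − 456 + 1 = −215 to 240 − 477 + 1 = −236 | 240 |
| 449 | 449 − 456 + 1 = −6 to 449 − 477 + 1 = −27 | 449 |

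The formula is always ≤ 0 here, because every such sample precedes the first active dose. The sign of the carried-over value depends on the assumed origin.

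**Step 4: the period.** Former-placebo patients never had an ISIS 420915 dose in the parent study, so the start in SAP 3.2.1.1.4 does not exist for them. The table rule in SAP 3.2.1.4 does supply a start, but for this group it is the first placebo dose. A programmer who fills the gap from 3.2.1.4 brings placebo-period samples into their IM status.

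**The case against.** The best defence is that the intent is visible. SAP 3.6.2 sets pre-existing antibodies apart, lists sample results during and after treatment with ISIS 420915, describes the first positive as one arising since that treatment, and confines transient and persistent classes to treatment-induced antibodies. SAP 3.2.1.1.4 ties IM status to ISIS 420915, and SAP 3.2.1.4 can be read as saying only what the tables display. On this view the Day 1 conflict is a one-day slip with almost no scheduled cases, and the carry-over depends on a CS2 plan that we cannot see: placebo patients may not have been given an IM status there at all.

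Much of this stands, and it limits the point. It does not settle which rule applies. The carry-over in 3.2.1.1.6 still has no arm restriction, and the period meant to define IM status still has no start for one whole group.

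A reader might also infer more than the documents support:
- That SAP 9.2.2.2 is a further contradictory definition. It is limited to the combined summaries and expressly disclaims conflict with 3.2.1.1.4.
- That transient and persistent classes are firm outputs. SAP 3.6.2 makes them discretionary.
- That antibody incidence in former-placebo patients is inflated by a known amount. With a 1–2% chance of a confirmed positive per sample and 4–8 samples, 45 × (1 − (1 − f)^k) runs from 1.8 to 6.7 patients. Both inputs are guesses. The formula treats a patient's samples as independent, although cross-reactive antibodies would tend to persist. The 45 is the planned CS2 placebo allocation, not the number entering or tested in this study.

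**Conclusion.** Wrong as written, and cheap to correct. The Day 1 conflict is certain, since it is arithmetic on the SAP's own text, but it should affect few patients. The missing period start for former-placebo patients and the unrestricted carry-over are also plain in the text. Read literally, SAP 3.2.1.1.6 and 3.2.1.4 together can give a former-placebo patient an IM-positive status and an onset from a time before any active drug.

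Whether the carried-over onset is actually positive, and whether any placebo patient was IM positive in CS2, depends on the CS2 plan. The number of patients affected cannot be estimated from the documents. The outputs are descriptive, and no hypothesis test or sample size rests on them. The documents show conflicting rules that allow misclassification; they do not show that misclassification occurred.

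**What to change.** For the OLE outputs:
- Start the IM-status period for every patient after the first dose on Day 1 of ISIS 420915. SAP 9.2.2.2 already uses Day 1 for the combined outputs; add that pre-dose samples do not count. Align 3.2.1.1.4 and 3.2.1.4 with this. CS2 visits can still be displayed.
- Limit the carry-over in 3.2.1.1.6 to patients who received ISIS 420915 in the parent study.
- Report confirmed positives at or before the first active dose separately as pre-existing, and leave them out of onset summaries and any treatment-induced classes.
- Reconcile the Day 1 rule in one of two ways. Either drop the added day for pre-dose samples, so that Day 1 pre-dose is 0 and the day before is −1. Or narrow the condition to samples before Day 1 and add an explicit rule for Day 1 pre-dose samples.

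Testing retained Day 1 PK plasma from former-placebo patients would supply the missing pre-exposure result. It is optional, already permitted by 3.6.2, and depends on the plasma having been kept.

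The cost is SAP wording and a re-derivation of IM status and onset, with possibly slightly fewer patients counted as treatment-induced.

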5.1 Interim Analysis at EOT of the Parent Study

A planned interim analysis of the OLE study based on cleaned database will be performed after all patients in the parent study have completed EOT assessments and the parent study is unblinded according to CS2 unblinded plan.

The following will not be performed as part of this interim analysis:

- Summaries using PPS
- The review of protocol deviations to identify those leading to exclusion from the PPS

The table below lists what data will be included in the summary output by endpoint type and what output is planned for this interim analysis at the parent study EOT.

Provided at interim of OLE study (at parent study EOT)	Comment
Patient Characteristics	
• Summaries of patient disposition, protocol deviations, analysis sets.	- For all enrolled patients
Summary of demographic characteristics and baseline characteristics and exposure to Study Drug.	- For SS
Concomitant medication.	- On-study summary for SS
The longitudinal safety analysis of exposure to Study Drug.	- For LSS
• Corresponding listings.	
Efficacy and PD	
By visit summary table for each endpoint, Include summary statistics (absolute, change and/or percent change from baselines) based on both the parent study baseline and the OLE study baseline.	- On-treatment summary for FAS
 Boxplot of Absolute Value, Change from Baseline, and/or Percent Change from Baseline over Time based on both the parent study baseline and the OLE study baseline. 	 On-treatment summary for FAS Only plot time points where at least 20% of the CS3 population have data
• Summary table and figure for Response Rate by Threshold Value by Visit.	- On-treatment summary for FAS
• Corresponding listings.	- All results collected in CS3 before IA data cut
Safety Endpoint	
• Summary tables for AE.	- On-Treatment and On-Study for SS
• Summary tables of safety lab, vital sign, ECG, ERG by visit.	- On-Treatment+ Post-Treatment for SS
• Summary table and shift table of abnormal safety lab results, ECG worst values and stopping rules.	- Abnormal safety lab is on-study for SS
• The longitudinal safety analysis of AE and abnormal safety lab results, including hepatobiliary, platelets and renal parameters.	- For LSS
Corresponding listings.	- All results collected in CS3 before IA data cut
Immunogenicity	

Provided at interim of OLE study (at parent study EOT)	Comment
 Summary table for sample IM status, anti-ISIS 420915 antibody titer values, patient IM status, onset and peak titer of the ADA, time to reach peak titer. Box Plot of Titer over Time. 	- On-study summary for SS
 mNIS+7, Norfolk total score and TTR summary by patient IM status. Box plot for mNIS+7 and Norfolk totalscore by patient IM status. 	 Efficacy is on-treatment for FAS Patient IM status ison-study for SS
Summary table of AE by patient IM status.	 AE is on-treatment and On-Study for SS Patient IM status is on-study for SS
Summary table and shift table of abnormal safety lab results by patient IM status.	 Abnormal safety lab is on-study for SS Patient IM status ison-study for SS
Corresponding listings.	- All results collected in CS3 before IA data cut
PK	
Summary table of ISIS 420915 Trough Plasma Concentrations (ng/mL) with and without Stratification by prior treatment in the parent study and Subject Immunogenicity Status	- On-study for PK set
 Figure of Mean (±SD) of ISIS 420915 Plasma Trough Concentrations (ng/mL) over Time by prior treatment in the parent study and Subject ImmunogenicityStatus 	 On-study for PK set plot time points where at least 20% of the CS3 population have data
Corresponding listings	- All results collected in CS3 before IA data cut

